7.3.2. Autonomic Monitoring

All peripheral autonomic physiological signals will be collected at 400 Hz using Chart Data Acquisition Software (ADInstruments) on a laptop equipped with a 16-channel Powerlab DAQ System (ADInstruments). Skin conductance level will be measured with MRI-compatible bipolar Ag/AgCl finger electrodes (MLT117F, ADInstruments) placed on the palmar aspect of the second and fourth fingers of the nondominant (left) hand, prior to the MRI session. Subjects' ECG signal will be collected with an MRI-compatible Patient Monitoring system (Biopac 150, Biopac Systems Inc.) through MRI-compatible electrodes (VerMed, Bellows Falls) placed on the chest.

7.3.3. Nausea severity psychophysics

Nausea ratings will be collected during motion sickness provocation using a 0-4 numerical rating scale (NRS). One member of the team will instruct the subject on how

to use the button box to rate his/her nausea sensation. For the mock scanner training, once every 15 seconds, a sensory cue will be applied, reminding the subject to rate their nausea severity. During the actual fMRI experiment, subjects will rate nausea severity using the button box, as they experience it, and ratings increase events will be used to guide data analysis. We will ask the subject to press buttons on a MRI compatible button-box to rate nausea using the following scale:

- Press the thumb button if you do not feel any nausea;
- Button 1 (index finger) if **minimal** nausea is experienced;
- Button 2 (middle finger) if **mild** nausea is experienced;
- Button 3 (ring finger) if **moderate** nausea is experienced;
- Button 4 (pinky finger) if **severe** nausea is experienced;

The subject will be instructed that, when button 4 is pressed, signifying that severe nausea is experienced, the nauseating stimulus (moving lines) will be stopped. If, due to any reason, the subject wants to stop the experiment before, he/she can squeeze the squeeze bulb, the experiment will stop and the subject will be taken out of the mock or real fMRI magnet.

7.3.4. Subject assessment of nausea

Motion Sickness Assessment Questionnaire (MSAQ)

Following the visual nauseogenic task, subjects will complete the Motion Sickness Assessment Questionnaire (MSAQ) ([Appendix 8](#)), which quantifies the severity of different dimensions of nausea induced by motion sickness [[Gianaros, 2001](#)]

Visual Analogue Scale (VAS)

Each subject will complete a VAS to record their perception of stomach fullness, hunger, nausea, bloating and abdominal pain. The VAS ([Appendix 7](#)) will be represented by lines, 100mm in length, anchored with words describing the most negative rating on the left and the most positive rating on the right. The site will be provided with paper copies of the scale to administer at each MRI session. Subjects will complete a VAS form approximately 30 min before and approximately 30 min after each imaging scan session.

7.3.5. Electrogastrogram

Electrogastrography (EGG) is a technique for recording gastric myoelectrical activity using cutaneous electrodes (non-invasively) by placing three EKG-type electrodes in the epigastrium in standard positions. Signals will be obtained with appropriate amplification and filtering during the MRI scans. The EGG summates the ongoing gastric slow wave and plateau potential activity of the stomach. Collection of EGG during the MRI is experimental and may not progress if deemed uninterpretable.

7.4. Safety

Planned time points for all safety assessments are listed in the Time and Events Table (Section [7.1](#)). Additional time points for safety tests such as vital signs, physical exams

and laboratory safety tests may be added during the course of the study based on newly available data to ensure appropriate safety monitoring.

7.4.1. Adverse Events (AE) and Serious Adverse Events (SAEs)

The definitions of an AE or SAE can be found in [Appendix 3](#) (Section 12.3).

The Investigator and their designees are responsible for detecting, documenting and reporting events that meet the definition of an AE or SAE.

Nausea during the visual nauseogenic task is expected and will not be considered an AE, and will be reported as an endpoint. Any other untoward medical events occurring during the visual nauseogenic task should be reported as an AE/SAE if meets the definition as noted in [Appendix 3](#) (Section 12.3).

7.4.1.1. Time period and Frequency for collecting AE and SAE information

- Any SAEs assessed as related to study participation (e.g., protocol-mandated procedures, invasive tests, or change in existing therapy) or related to a GSK product will be recorded from the time a subject consents to participate in the study up to and including any follow-up contact.
- AEs will be collected from the start of Study Treatment until the follow-up contact, at the timepoints specified in the Time and Events Table (Section 7.1).
- Medical occurrences that begin prior to the start of study treatment but after obtaining informed consent may be recorded on the Medical History/Current Medical Conditions section of the CRF.
- All SAEs will be recorded and reported to GSK within 24 hours, as indicated in [Appendix 3](#).
- Investigators are not obligated to actively seek AEs or SAEs in former study subjects. However, if the Investigator learns of any SAE, including a death, at any time after a subject has been discharged from the study, and he/she considers the event reasonably related to the study treatment or study participation, the Investigator must promptly notify GSK.

NOTE: The method of recording, evaluating and assessing causality of AEs and SAEs plus procedures for completing and transmitting SAE reports to GSK are provided in [Appendix 3](#).

7.4.1.2. Method of Detecting AEs and SAEs

Care will be taken not to introduce bias when detecting AEs and/or SAEs. Open-ended and non-leading verbal questioning of the subject is the preferred method to inquire about AE occurrence. Appropriate questions include:

- “How are you feeling?”
- “Have you had any (other) medical problems since your last visit/contact?”

- “Have you taken any new medicines, other than those provided in this study, since your last visit/contact?”

7.4.1.3. Follow-up of AEs and SAEs

After the initial AE/SAE report, the Investigator is required to proactively follow each subject at subsequent visits/contacts. All SAEs, and non-serious AEs of special interest (as defined in Section 4.6.1 and Section 7.4.1.4), will be followed until resolution, until the condition stabilizes, until the event is otherwise explained, or until the subject is lost to follow-up (as defined in Section 5.4). Further information on follow-up procedures is given in Appendix 3 (Section 12.3).

7.4.1.4. Adverse Events (AE) of Special Interest

In the Phase IV clinical development program, AEs of special interest included several areas of safety related concern for the T2DM population, particularly for a GLP-1R agonist such as albiglutide. Specific eCRF pages will be used to capture additional details for the following AEs of special interest:

- Hypoglycemic events
- Liver events
- CV events
- Injection site reactions
- Potential systemic allergic reactions
- Pancreatitis
- Medullary thyroid cancer
- Pneumonia
- Atrial fibrillation/atrial flutter

The following additional AEs of special interest will be captured in the AE eCRF pages:

- GI events
- Malignant neoplasms, including pancreatic cancers
- Appendicitis

7.4.1.5. Regulatory Reporting Requirements for SAEs

Prompt notification by the Investigator to GSK of SAEs related to study treatment (even for non-interventional post-marketing studies) is essential so that legal obligations and ethical responsibilities towards the safety of subjects and the safety of a product under clinical investigation are met.

GSK has a legal responsibility to notify both the local regulatory authority and other regulatory agencies about the safety of a product under clinical investigation. GSK will comply with country specific regulatory requirements relating to safety reporting to the regulatory authority, Institutional Review Board (IRB)/Independent Ethics Committee (IEC) and Investigators.

Investigator safety reports are prepared for suspected unexpected serious adverse reactions according to local regulatory requirements and GSK policy and are forwarded to investigators as necessary.

An investigator who receives an investigator safety report describing a SAE(s) or other specific safety information (e.g., summary or listing of SAEs) from GSK will file it with the IB and will notify the IRB/IEC, if appropriate according to local requirements.

7.4.2. Pregnancy

- Details of all pregnancies in female subjects will be collected after the start of dosing and until the follow-up visit.
- If a pregnancy is reported then the Investigator should inform GSK within 2 weeks of learning of the pregnancy and should follow the procedures outlined in [Appendix 4](#).

7.4.3. Hypoglycemia

Although not anticipated in the healthy volunteer population, hypoglycemia is a risk with treatment of a GLP-1 receptor agonist. Capillary blood glucose measures will be taken after each post dose MRI. A capillary blood glucose measure should be taken any time a subjects present with signs and or symptoms of hypoglycaemia and the subject treated with dietary therapy (i.e. a small meal), a carbohydrate load (e.g., glucose tables or orange juice), or any other required treatment at the discretion of the Investigator. Subjects will be asked to eat a snack after the investigational drug administration sessions.

7.4.4. Physical Exams

- A complete physical examination will include, at a minimum, assessment of the Cardiovascular, Respiratory, Gastrointestinal and Neurological systems and skin. Height and weight will also be measured and recorded.
- A brief physical examination will include, at a minimum assessments of the skin (including injection site), lungs, cardiovascular system, and abdomen (liver and spleen).
- Height weight and body mass index will be measured and recorded at screening only. Height and weight should be measured with the subject in indoor daytime clothing with no shoes.

7.4.5. Discharge

Subjects will remain at the clinic for at least 1.0 hours after the dose of medication or completion of scan whichever is later. All procedures and assessments must be complete before the subject is released. The Investigator or medically qualified site staff will approve the release of the subject from the clinic or will provide treatment as per standard of care as required.

7.4.6. Vital Signs

- Vital signs will be measured in semi-supine position after 5 minutes rest and will include systolic and diastolic blood pressure and pulse rate.

- For all vital signs, single measurement will be performed at time points specified in Time and Events Tables (Section 7.1).
- Vital sign measurements can be repeated once if clinically significant changes or machine error occur. Out of range blood pressure and heart rates will be repeated at the Investigator's discretion.

7.4.7. Electrocardiogram (ECG)

- Single 12-lead ECGs will be obtained at screening using an ECG machine that automatically calculates the heart rate and measures PR, QRS, QT, and QTc intervals. Refer to Section 5.4.2 for QTc withdrawal criteria and additional QTc readings that may be necessary.

7.4.8. Clinical Safety Laboratory Assessments

All protocol required laboratory assessments, as defined in Table 1, must be conducted in accordance with the Laboratory Manual, and Protocol Time and Events Schedule. Laboratory requisition forms must be completed and samples must be clearly labelled with the subject number, protocol number, site/centre number, and visit date. Details for the preparation and shipment of samples will be provided by the laboratory and are detailed in the SRM. Reference ranges for all safety parameters will be provided to the site by the laboratory responsible for the assessments.

If additional non-protocol specified laboratory assessments are performed at the institution's local laboratory and result in a change in subject management or are considered clinically significant by the Investigator (e.g., SAE or AE or dose modification) the results must be recorded in the CRF.

Refer to the SRM for appropriate processing and handling of samples to avoid duplicate and/or additional blood draws.

All study-required laboratory assessments will be performed by a central laboratory, entered into the eCRF and sent to GSK via lab data transfer.

Haematology, clinical chemistry, urinalysis and additional parameters to be tested are listed in Table 2

Table 2 Protocol Required Safety Laboratory Assessments

Laboratory Assessments	Parameters		
Haematology	Platelet Count	RBC Indices:	WBC count with Differential:
	RBC Count	MCV	Neutrophils
	Hemoglobin	MCH	Lymphocytes
	Hematocrit		Monocytes
			Eosinophils
			Basophils

Laboratory Assessments	Parameters			
Clinical Chemistry ¹	BUN	Potassium	AST (SGOT)	Total and direct bilirubin
	Creatinine • eGRF (MDRD)	Sodium	ALT (SGPT)	Total Protein
	Glucose	Calcium	Alkaline phosphatase	Albumin
Glycemic parameters	Capillary blood glucose (for patient safety only)			
	Fasting plasma glucose			
Routine Urinalysis	
 • Specific gravity • pH, glucose, protein, blood and ketones by dipstick • Microscopic examination (if blood or protein is abnormal) 			
Other Screening Tests	
 • TSH, free T4, triglycerides, amylase and lipase • HIV, Hepatitis B and C Screen • Alcohol/Cotinine and drug screen (to include at minimum: amphetamines, barbiturates, cocaine, opiates, cannabinoids and benzodiazepines) • Serum or urine hCG Pregnancy test (as needed for women of child bearing potential) ² • FSH and estradiol-for women < 60 yrs and <12 months postmenarchal and do not agree to effective method of birth control 			

NOTES :
 
 1. Details of Liver Chemistry Stopping Criteria and Required Actions and Follow-Up Assessments after liver stopping or monitoring event are given in Section 5.4.1 and Appendix 2. 2. Local urine testing will be standard for the protocol unless serum testing is required by local regulation or ethics committee. 				

All laboratory tests with values that are considered clinically significantly abnormal during participation in the study or within 25 days after the last dose of study treatment should be repeated until the values return to normal or baseline. If such values do not return to normal within a period judged reasonable by the Investigator, the etiology should be identified and the sponsor notified.

7.5. Tracking of Albiglutide and Exenatide Pen Injector Failures and User Errors

All albiglutide pen injector failures and user errors must be detected, documented, and reported by the Investigator throughout the study. Detailed information on albiglutide pen injector failures and user errors will be collected on the Albiglutide Injector Pen and Reporting Form.

For both, albiglutide and exenatide pen injector failures and user errors associated with or resulting in events fulfilling the definition of an AE or SAE will follow the processes outlined in Section 7.4.1.

8. DATA MANAGEMENT

For this study, subject data will be entered into GSK defined electronic CRFs, transmitted electronically to GSK or designee, and combined with data provided from other sources in a validated data system.

Management of clinical data will be performed in accordance with applicable GSK standards and data cleaning procedures to ensure the integrity of the data, e.g., removing errors and inconsistencies in the data.

Adverse events terms and concomitant medications will be coded using MedDRA (Medical Dictionary for Regulatory Activities) and an internal validated medication dictionary, GSKDrug.

CRFs (including queries and audit trails) will be retained by GSK, and copies will be sent to the Investigator to maintain as the Investigator copy. Subject initials will not be collected or transmitted to GSK according to GSK policy.

9. STATISTICAL CONSIDERATIONS AND DATA ANALYSES

The study has 2 parts – Part A and Part B. After Part A, a review of safety data as well as fidelity of imaging and physiological (e.g. EGG) measures taken during the different MRI scan sessions will be performed. Part A data review is part of the exploratory nature of this study and could result in refinement of endpoints and statistical analysis. A decision to enroll 4 additional subjects, and/or adjust Part B design (e.g., change in MRS pulse sequence), will be made based on imaging evaluators' judgment in consultation with the PI and Sponsor.

9.1. Hypotheses

No primary hypothesis will be pre-specified due to the exploratory nature of the study.

9.2. Sample Size Considerations

A total from Parts A and B of 24 or 28 randomized subjects with valid MRI data that could be pooled for analysis will be targeted for the entire study. Part A will initially randomize 4 subjects. Based on data review from the initial 4 subjects, additional 4 subjects may be randomized for Part A. The decision to enroll another Cohort of 4 subjects in Part A will be based on imaging evaluators' judgment in consultation with the PI and Sponsor.

Part B will randomize 20 subjects.

Subjects will be randomized according to treatment sequences described in Section 4.2.

9.2.1. Sample Size Assumptions & Size Sensitivity

Accurate prospective determination of experimental power and sample size is difficult for fMRI experiments because many idiosyncratic factors (e.g. scanner sequence, brain region under investigation, task paradigm) can have a large influence on the effective signal-to-noise. In addition, there is little similar published work available to act as a guide. A target sample size in the range 12 to 24 is recommended by Desmond and Glover [Desmond, 2002] for fMRI experiments; though it should be noted that advances in acquisition technology and analysis techniques in the last thirteen years have significantly increased signal-to-noise, meaning the upper bound of the estimate ($N \approx 24$) may now be somewhat inflated. Importantly, the sample size chosen for this study is consistent with the sample size previously published by the Martinos Center group in their nausea neuroimaging study [[name], 2013].

9.2.2. Sample Size Re-estimation or Adjustment

If subjects prematurely discontinue the study or individual subject technical issues arise, subjects will be replaced at the discretion of the imaging evaluators' judgment in consultation with the Investigator and Sponsor. Subjects will be assigned to the same treatment sequence in order to meet the target number of subjects. Within each phase or part, the randomization of subjects should first be completed before subjects are replaced. Data from subjects who are replaced will be used only for safety analysis.

Issues that may lead to exclusion of data from analysis could include excessive head-motion by the subject during a scan, identifiable artifacts on the brain images arising from problems with the scanner, and issues with the simultaneous physiological recordings (poor signals due to interference, or sensors moving out of position during a scan). Data quality will be iteratively assessed by technical imaging site staff throughout the study in a blinded manner. If some subjects' data is sub-standard and therefore needs to be excluded, additional recruiting and testing may be conducted. Data quality findings will be documented.

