4.3. Type and Number of Subjects

This study will enrol both male and female healthy volunteers 18-50 years old who are right handed and sensitive to motion sickness. Approximately 60 healthy adults will be screened to achieve a total (from Parts A and B) of 24 or 28 randomized subjects.

In Part A, approximately 10 healthy adults will be screened to achieve 4 randomized. An additional 4 subjects (Cohort 2) may be randomized if changes to the acquisition parameters and scanning paradigm require confirmation before progressing to Part B.

If subjects prematurely discontinue the study or individual subject technical issues arise, subjects may be replaced at the discretion of the Investigator or imaging evaluators in consultation with the Sponsor. Subjects will be assigned to the same treatment sequence in order to meet the target number of subjects.

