5.4. Withdrawal/Stopping Criteria

A subject may withdraw from the study at any time at his or her own request, or may be withdrawn at any time at the discretion of the Investigator or the Sponsor for safety, behavioral, or administrative reasons. Safety data will be reviewed by the Sponsor in-stream by single case and collectively. If a safety concern arises, a decision about continuation of the study will be made.

Any subject presenting with nausea symptoms on the day of the off-therapy MRI or who had vomited within 12 hours prior to the scheduled off-therapy MRI session visit can be rescheduled for the visit or withdrawn at the Investigator's discretion.

Subjects who cannot complete any of the study procedures may be replaced at the discretion of the Investigator after consultation with the Sponsor.

A subject **MUST** be withdrawn from the study for the reasons including, but not limited to:

- Any AE, which, in the opinion of the Investigator precludes effective participation of the subject or poses a safety concern

The following AEs **will** require withdrawal:

- Confirmed pancreatitis
 - Pancreatic cancer.
 - Confirmed MTC or other thyroid C-cell neoplasia.
 - Liver chemistry abnormalities exceeding the threshold criteria outlined in [Appendix 2](#)
 - Severe allergic/hypersensitivity reactions that are considered by the Investigator to be attributable to investigational product or without a likely alternative aetiology.
 - QTc stopping criteria (see Section [5.4.2](#))
 - AE, which, in the opinion of the Investigator, requires withdrawal
 - Severe hypoglycemia, which, in the opinion of the Investigator or medical monitor, requires withdrawal
- Consent withdrawn
 - Lost to follow-up
 - Termination of study by sponsor
 - Pregnancy
 - Any untoward findings during the MRI scan that may jeopardize the imaging analysis or subject safety.

A subject **MAY** be withdrawn from the study for the reasons including, but not limited to:

- Nausea or vomiting requiring the use of anti-emetics or other interventions
- Protocol deviation (the Investigator should discuss the protocol deviation with the medical monitor before withdrawing a subject)
- Noncompliance with study visit schedule, as determined by the Investigator in consultation with the sponsor
- Other: the reason must be documented on the electronic Case Report Form (eCRF)

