6.4. Blinding

This will be a single blind (GSK and site staff are unblinded but subjects and imaging evaluators of MRI are blinded) study and the following will apply. Evaluators in this study are staff who analyze neuroimaging data. Every attempt will be made to maintain the single-blind. Exenatide placebo is not available for this study. An injection of saline using the same needle size will be given to the subjects who will be blind-folded at the time they receive the injection.

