4. ANALYSIS POPULATIONS

Population	Definition / Criteria	Analyses Evaluated
All Screened	
 • All participants who were screened will be considered for this population. This population will be used for summarizing screening status 	
 • Screen failure
Enrolled	
 • All participants who were successfully screened and enrolled for the trial and for whom a record exists on the study database. 	
 • Study population
Safety	
 • Comprise of all subjects who receive at least one dose of study treatment. • This population will be based on the treatment the subject actually received. • This population will include subjects who were replaced due to imaging data being invalid or not evaluable but received study drug. 	
 • Safety
Analysis Set (Randomised)	
 • Comprise of all randomized subjects who receive treatment and with valid imaging data, that will be determined by Martinos. • Subjects who are replaced are excluded from this population. 	
 • Imaging (Mechanism of Action)

NOTES :

- Please refer to Appendix 7: List of Data Displays which details the population to be used for each display being generated.

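### Every replaced subject leaves the imaging analysis whether or not the scans are valid, so a discretionary replacement after a nausea-related withdrawal can discard valid scans

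*Protocol*

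**What the plan says.** **The exclusion.** Protocol 9.2.2: "Data from subjects who are replaced will be used only for safety analysis". SAP section 4 defines the imaging Analysis Set as randomised, treated subjects with valid imaging data, and then adds as a separate item: "Subjects who are replaced are excluded from this population". Neither sentence carries a condition on scan validity.

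**The trigger and who decides.** There are three versions.
- Protocol 9.2.2: "If subjects prematurely discontinue the study or individual subject technical issues arise", then "subjects will be replaced at the discretion of the imaging evaluators", in consultation with the Investigator and Sponsor.
- Protocol 4.3, for the same triggers: "subjects may be replaced at the discretion of the Investigator or imaging evaluators in consultation with the Sponsor".
- Protocol 5.4: "Subjects who cannot complete any of the study procedures may be replaced at the discretion of the Investigator after consultation with the Sponsor".

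**The route through nausea.** Protocol 5.4 lists, among reasons for which a subject may (not must) be withdrawn: "Nausea or vomiting requiring the use of anti-emetics or other interventions".

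**Blinding.** Protocol 6.4: "GSK and site staff are unblinded but subjects and imaging evaluators of MRI are blinded".

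**Other statements on inclusion.** Protocol 9.3 lets partial completers into analyses that their data can support. Protocol 9.3.1 and the SAP synopsis define the analysis set by valid data and do not mention replacement. SAP 7.1.1 bases the primary efficacy analyses on all randomised subjects unless otherwise specified.

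**The concern.** Replacing a subject to reach a target number is one decision. Using or discarding the scans already acquired is another. The plan ties them together, so the replacement decision, not the quality of the scan, settles whether a valid scan counts.

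That decision can be related to outcome. The trial studies brain responses associated with nausea, and nausea needing intervention is a permitted reason for withdrawal. A valid scan can already exist by then: the post-dose scan starts about 1 hour after the Day 8 injection (Time and Events, footnote h), the exenatide nausea figure cited in Protocol 4.4 covers 24 hours, and a washout of 6 to 9 weeks follows before Session 2. If the subjects with the strongest response leave and are replaced, those retained are a milder group.

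At stake in the protocol's plan are the drug versus off-therapy contrasts, the separate analysis of subjects who perceived nausea on drug (Protocol 9.3), and the group map from the off-therapy nauseogenic task that defines the regions of interest.

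**Working it through.** **1. The plan's own number.** The target in Protocol 9.2 is a sum, not a power calculation: 4 + 20 = 24, or 8 + 20 = 28. No dropout or replacement rate is given.

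**2. Does any text limit the exclusion to invalid scans?** The nearest is the Safety population entry in SAP section 4, which says that this population takes in dosed subjects who were replaced because their imaging was invalid or could not be evaluated. It suggests that the authors had failed imaging in mind. It governs entry to the Safety set, however, and puts no condition on the exclusion from the imaging set. Protocol 9.2.2 also allows replacement after discontinuation alone.

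Neither document says whether validity is judged per scan or per subject. If per subject, the exclusion adds nothing for those replaced for failed imaging, and the point rests on the discontinuation route.

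**3. What one replaced subject loses** (Protocol Table 1, all scans valid):

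| Discontinues after | Sequence | Scans lost | Within-subject contrasts lost |
|---|---|---|---|
| Session 1 | 1 | 2 (off-therapy, albiglutide) | albiglutide − off-therapy |
| Session 1 | 3 | 2 (off-therapy, exenatide) | exenatide − off-therapy |
| Session 1 | 2 or 4 | 1 (post-dose) | none |
| Session 2 imaging, before follow-up | any | 3 | both drug − off-therapy and albiglutide − exenatide |

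The last row arises because Protocol 5.5 counts a subject as completed only after the follow-up visit. In sequences 1 and 3 the off-therapy scan lost after Session 1 includes the task run that feeds the region-of-interest map.

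**4. Illustrative size, Session 1 route only.** Let r be the number replaced after a valid Session 1, as a share of the target N. Assume equal allocation (N/4 per sequence) and replacements who complete in the same sequence (Protocol 4.3 and 9.2.2). The analysis set then still holds N pairs per drug and 3N scans, and the discarded data are additional.

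- Discarded pairs per drug = (N/4)r, as a share of N + (N/4)r.
- Discarded scans = (N/4)r × (2 + 1 + 2 + 1) = 1.5Nr, as a share of 3N + 1.5Nr.

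| r (assumed) | Pairs per drug, N = 24 | Scans, N = 24 | Pairs per drug, N = 28 | Scans, N = 28 |
|---|---|---|---|---|
| 5% | 0.3 of 24.3 (1.2%) | 1.8 of 73.8 (2.4%) | 0.35 of 28.35 (1.2%) | 2.1 of 86.1 (2.4%) |
| 10% | 0.6 of 24.6 (2.4%) | 3.6 of 75.6 (4.8%) | 0.7 of 28.7 (2.4%) | 4.2 of 88.2 (4.8%) |
| 20% | 1.2 of 25.2 (4.8%) | 7.2 of 79.2 (9.1%) | 1.4 of 29.4 (4.8%) | 8.4 of 92.4 (9.1%) |

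These are counts of data, not bias. Sizing the selection would need the withdrawal rate among nauseated subjects, the share of those replaced, and the relation of nausea to each imaging measure. The documents give none of these.

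**5. The reported Part A.** According to SAP 2.1, Part B was cancelled, four subjects completed Part A, and group analysis of the four was dropped. No replacement is reported. GI-VAS and MSAQ Tables 3.4 and 3.5 use the Safety population. Listings 22 to 24 use the Analysis population, so a replaced subject would appear in those summaries but not in the listings.

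**The case against.** The case against runs as follows.

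- **Only failed imaging was meant.** The one reason for replacement that the SAP states is invalid or non-evaluable imaging. This is fair evidence of intent, but the exclusion is written without that limit and the protocol names a second trigger.
- **The documents do not contradict each other.** This stands. A partial completer may be analysed unless replaced, and the texts can be read together that way. A reader might infer a flat contradiction; the documents do not support one. What the combined reading does is make the replacement decision settle inclusion.
- **The path is a chain of optional steps.** It takes a valid scan, then a withdrawal that may happen, then a discretionary replacement. In Protocol 9.2.2 the judgement belongs to the blinded evaluators. This also stands: a reader might infer that unblinded staff decide alone under 9.2.2, but there they are only consulted. Sections 4.3 and 5.4, however, give the Investigator the decision or a share in it.
- **The planned sample is not reduced.** Correct. Replacement restores the target, so discarded data must not be read as losses from the 24 or 28. Replacement does not undo selection, because those retained are still the subjects who stayed.
- **It hardly matters for the trial as reported, and much of the remedy exists.** Largely correct. Blinded quality review is already in Protocol 9.2.2, and Listings 2 and 4 show withdrawals and subjects excluded from any population.

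**Conclusion.** The point holds as a weakness of the rule. Followed as written, the plan can discard valid scans through a discretionary decision that may be related to nausea and on which unblinded parties are consulted. The volume is modest: under the assumed 5% to 20% of subjects replaced after Session 1, 1.2% to 4.8% of the available pairs per drug and 2.4% to 9.1% of the available scans. The figures rest on equal allocation and on replacements who complete, and they leave out discontinuation after Session 2 imaging. The main concern is selection, whose size the documents do not allow to be estimated.

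Two stronger readings should be resisted. A reader might infer that the Part A results are biased. With group analysis dropped and no replacement reported, the effect there is probably nil. The SAP attachment still describes a paired off-therapy versus exenatide test, which sits uneasily with SAP 2.1, but that is a separate matter. A reader might also infer that the albiglutide versus exenatide comparison is generally at risk. A Session 1 withdrawal never supplies that difference; only a subject replaced after Session 2 imaging could lose it.

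Priority is minor for the reported Part A. The rule would matter more in any study that reused this design.

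**What to change.** Replace the two exclusion sentences (Protocol 9.2.2 and SAP section 4) with:

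> Replacement does not by itself remove a subject from the imaging analysis. Valid scans from randomised and dosed subjects, replaced or not, are used in each contrast they can support. Scans are excluded only by the blinded quality check, or for important deviations judged blind to treatment and nausea outcome.

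The deviation clause leaves room to set aside scans affected by, for example, prohibited medication.

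Put Listings 22 and 23 on the Safety population to match Tables 3.4 and 3.5, and include replaced subjects' scans in Listing 24. Existing Listings 1, 2, 4 and 9 can be used to show who was replaced and why. Protocol 4.3, 5.4 and 9.2.2 must be reconciled on who decides replacement. No change to the clinical withdrawal rules is proposed.

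The cost is two sentences, the population of three listings and a small blinded review of deviations. The analysis would carry slight sequence imbalance and some incomplete subjects. No new subjects, scans or listings are needed.
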